16.3 Sample Size, Accrual Rate and Power and Significance Level

- 16.31 Sample Size: This study is expected to require a minimum of 10 and a maximum of 28 evaluable patients. We anticipate accruing 3 (10%) additional patients to account for ineligibility, cancellation, major treatment violation, or other reasons. Therefore, the study is expected to accrue a maximum of 31 patients overall. **As per Amendment 4, accrual will cease at 10 patients.**
- 16.32 Accrual Rate and Study Duration: The anticipated accrual rate is 10 evaluable patients per year. Therefore, the accrual period is expected to be 3.1 years. The

primary endpoint will be evaluated approximately 3.75 years after the trial opens, or after the last patient accrued has received 24 months of treatment.

16.33 Power and Significance Level: Assuming that the number of successes is binomially distributed, the significance level is .10, i.e. there is a 10% chance of finding the drug to be effective when it truly is not. The probability of declaring that this regimen warrants further study (i.e. statistical power) under various

success proportions and the probability of stopping accrual after the interim analysis can be tabulated as a function of the true success proportion.

If the true success proportion is...	0.15	0.20	0.25	0.30	0.35
Then the probability of declaring that the regimen warrants further study is...	0.456	0.624	0.756	0.851	0.914
and the probability of stopping after the interim analysis is ...	0.544	0.376	0.244	0.149	0.086

16.34 Other considerations: Adverse events, quality/duration of response, and patterns of treatment failure observed in this study, as well as scientific discoveries or changes in standard care will be taken into account in any decision to terminate the study.

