16.0 Statistical Considerations and Methodology

16.1 Overview

This is a phase II study designed to assess the overall cutaneous response rate at cycle 9 in MF patients treated with pembrolizumab. It is a single one-stage design with an interim analysis based on the Simon optimal design with 85% power and 10% Type I error.

NOTE: As per Amendment 4, accrual will cease after the enrollment of 10 patients due to sponsor decision on funding. Thus, the study power and type I error will not be appropriate for the analysis, as the study will not be able to go to full accrual. The study will be analyzed at the pre-defined interim step.

16.11 Endpoint:

The primary endpoint is overall cutaneous response (cutaneous complete response (CR), cutaneous 90 response (CR90) or cutaneous partial response (PR)) as defined using the mSWAT score as stated in section 11.0. Throughout Section 16.0, CR, CR90 or PR will be considered synonymous with “success”, unless specified otherwise. All patients meeting the eligibility criteria who have signed a consent form and have begun treatment will be evaluable for response.

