16.2 Statistical Design

- 16.21 Design: The largest success proportion where the proposed treatment regimen would be considered ineffective in this population is 15%, and the smallest success proportion that would warrant subsequent studies with the proposed regimen in this patient population is 35%. This design uses 28 evaluable patients to test the null hypothesis that the true complete response rate is at most 15%.
- 16.22 Interim Analysis: Enter 10 evaluable patients to the study. If there are less than 2 successes in the first 10 evaluable patients, we will consider this regimen ineffective in this patient population and terminate this study. Otherwise, if the number of successes is at least 2, we will continue accrual.
- 16.23 **N/A as per Amendment 4:** Final Decision rule: If 6 or fewer successes are observed in the first 28 evaluable patients, we will consider this regimen ineffective in this patient population. Otherwise, if the number of successes is at least 7, this will be considered evidence of promising activity and the treatment may be recommended for further testing in subsequent studies.
- 16.24 **N/A as per Amendment 4:** NOTE: We will not suspend accrual at the interim analysis to allow the first 10 patients to become evaluable, unless undue toxicity is observed. Given the limited overall sample size and the inclusion of an adverse events stopping rule, we feel it is ethical to not halt accrual for the interim analysis. However, if accrual is extremely rapid, we may temporarily suspend accrual in order to obtain safety data on these patients before re-opening accrual to further patients.

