16.4 Analysis Plan

16.41 Primary Outcome Analysis: The mSWAT score at baseline and cycle 9 will be used for change in baseline calculations. All calculated values will use the last-observation-carried forward for any participants who withdraw, are lost to follow up, or exit the study per protocol. The proportion of successes will be estimated by the number of successes divided by the total number of evaluable patients will be analysed using Mann-Whitney U for nonparametric data and the student t-test. Confidence intervals for the true success proportion will be calculated according to the approach of Duffy and Santner (Duffy D 1987).

16.42 Secondary Outcome Analysis: These analyses will include all patients meeting the eligibility criteria who have signed a consent form and have begun treatment, including patients who fail to achieve a complete or partial response.

Adverse Events: All eligible patients that have initiated treatment will be considered evaluable for assessing adverse event rate(s). The maximum grade for each type of adverse event will be recorded for each patient, and frequency tables will be reviewed to determine patterns. Additionally, the relationship of the adverse event(s) to the study treatment will be taken into consideration.

Response Rates:

Changes in mSWAT scores from baseline will be evaluated at cycle 9. Summary statistics will be calculated.

Patients will be assigned response based on the mSWAT criteria in section 11.0. Proportions of patients will be calculated and described using summary statistics. Proportions of interest are patients having CR, CR90 and PR; patients having stable subcutaneous disease; patients having progressive cutaneous disease; and patients having an overall systemic response rate.

Progression free survival time is defined for all evaluable patients as the time from registration to relapse or death due to any cause. Patients are censored if they have not achieved a progression at the time of analysis. The distribution of progression-free survival will be estimated using the method of Kaplan-Meier. In addition, the progression-free survival rate at 5 years after registration will be reported.

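### Section 16.33 labels the chance of passing the interim look as statistical power: for the 28-patient design 0.456–0.914 should read 0.098–0.855, and the paragraph carries no Amendment 4 marking

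*Combined protocol and SAP*

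**What the plan says.** Section 16.1 describes a design based on Simon's optimal plan with 85% power and 10% type I error. Section 16.21 sets 15% as the highest rate regarded as ineffective and 35% as the lowest rate worth pursuing. Under 16.22 the study stops if fewer than 2 of the first 10 evaluable patients succeed; "Otherwise, if the number of successes is at least 2, we will continue accrual". The final rule in 16.23 is "If 6 or fewer successes are observed in the first 28 evaluable patients, we will consider this regimen ineffective in this patient population", and 7 or more counts as promising.

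Section 16.33 states that "the significance level is .10, i.e. there is a 10% chance of finding the drug to be effective when it truly is not". Its table then has two rows. The first is headed "Then the probability of declaring that the regimen warrants further study is" and the text above it equates that probability with power: "The probability of declaring that this regimen warrants further study (i.e. statistical power"). It reads 0.456, 0.624, 0.756, 0.851, 0.914 at true rates 0.15, 0.20, 0.25, 0.30, 0.35. The second row, for stopping at the interim, reads 0.544, 0.376, 0.244, 0.149, 0.086.

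Amendment 4 stops accrual at 10 patients. The note in 16.1 says that "the study power and type I error will not be appropriate for the analysis" and that the study will be analysed at the interim step. Sections 16.23 and 16.24 are tagged as not applicable and 16.31 has an added sentence. Section 16.33 has neither.

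**The concern.** A 10% false-positive chance and a 45.6% chance of a positive declaration at the null rate cannot both describe the same decision, yet they stand together in 16.33. Likewise 0.914 at 35% does not agree with the 85% power in 16.1. The two table rows also sum to 1.000 in every column. In a two-stage design they should not, because some trials pass the interim and then fail the final rule.

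What is at stake is the conclusion the 10-patient trial may draw. For 2 or more successes, 16.22 prescribes only further accrual, which is now impossible, so the plan attaches no conclusion to the result that is most likely if the drug works. The one phrase in the plan that fits the event is the table's heading about warranting further study. A report that borrowed it, beside an untagged .10 significance level, would be claiming activity on a bar that an ineffective regimen clears almost half the time.

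**Working it through.** **Inputs.** Null rate 0.15 and target rate 0.35 (16.21); continue if at least 2 of 10 (16.22); declare promising if at least 7 of 28 (16.23); target type I error 0.10 and power 0.85 (16.1). All probabilities are exact binomial.

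**Step 1: reproduce the printed rows.** The chance of stopping is P(X ≤ 1 | 10, p) = (1−p)^10 + 10p(1−p)^9.

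- p = 0.15: 0.1969 + 0.3474 = 0.5443, so the chance of passing is 1 − 0.5443 = 0.4557.
- p = 0.35: 0.0135 + 0.0725 = 0.0860, so the chance of passing is 1 − 0.0860 = 0.9140.

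Across the five rates, stopping is 0.5443, 0.3758, 0.2440, 0.1493, 0.0860, and passing is 0.4557, 0.6242, 0.7560, 0.8507, 0.9140. Both printed rows match to three decimals. The row called power is therefore P(at least 2 of 10) and nothing more.

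**Step 2: apply the full rule.** The probability of a positive conclusion is the sum over x = 2 to 10 of P(X1 = x | 10, p) × P(X2 ≥ 7−x | 18, p), where X2 counts successes in the remaining 18 patients. At p = 0.15:

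| x | P(X1 = x) | P(X2 ≥ 7−x) | product |
|---|---|---|---|
| 2 | 0.2759 | 0.1206 | 0.0333 |
| 3 | 0.1298 | 0.2798 | 0.0363 |
| 4 | 0.0401 | 0.5203 | 0.0209 |
| 5 | 0.0085 | 0.7759 | 0.0066 |
| 6 | 0.0012 | 0.9464 | 0.0012 |
| 7 or more | 0.0001 | 1 | 0.0001 |
| sum | | | 0.0984 |

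**Step 3: compare at every rate.**

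| True rate | 0.15 | 0.20 | 0.25 | 0.30 | 0.35 |
|---|---|---|---|---|---|
| Printed as power | 0.456 | 0.624 | 0.756 | 0.851 | 0.914 |
| Two-stage rule | 0.098 | 0.280 | 0.511 | 0.716 | 0.855 |
| Pass interim, fail final | 0.357 | 0.344 | 0.245 | 0.135 | 0.059 |

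The last row is the omitted part, taken from unrounded values (at 15%, 0.4557 − 0.0984 = 0.3573).

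**Step 4: try other readings.** Ignoring the interim, P(at least 7 of 28) is 0.115, 0.322, 0.572, 0.780, 0.908. Success conditional on passing the interim is 0.216, 0.449, 0.676, 0.841, 0.935. Neither gives the printed row.

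**Step 5: check the design.** A search over two-stage designs for 15% against 35%, with type I error at most 0.10 and power at least 0.85, returns the plan's own boundaries (stop at 1 or fewer of 10, reject at 6 or fewer of 28) as optimal: type I error 0.0984, power 0.8548, expected sample size under the null 10 + 18 × 0.4557 = 18.2. The targets in 16.1 and the .10 in 16.33 were right for that design.

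**The case against.** The best reply is that Amendment 4 has already dealt with this. The note in 16.1 names both power and type I error as inappropriate, it opens the statistical section, and 16.31, just above the table, repeats that accrual ends at 10. On that view 16.33 belongs to an abandoned design, and the missing tag is editorial. The printed numbers are also exactly right for the only rule still operating, so the fault is in the label. Nothing in the plan says that 2 of 10 will be reported as activity, 16.41 already plans a proportion and a confidence interval, and no sample size or boundary depends on the row. Finally, the fourfold discrepancy is confined to the 15% column; at 35% the gap is 0.059.

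Much of this is fair and limits the harm. The false-positive point does concern the 15% column alone; the other columns misstate the chance of a positive conclusion, by amounts that shrink as the true rate rises. The harm also depends on how the result is reported. But the note does not correct the row, which was already wrong for the 28-patient design. If the row is instead read as the live 10-patient rule, the .10 sentence is false, because that rule passes a 15% regimen 45.6% of the time. One of the two is wrong on either reading. Nor does the note say what 2 or more of 10 means.

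**Conclusion.** The concern holds and should be fixed. The row in 16.33 is the probability of continuing past the interim, mislabelled as power. For the 28-patient design the correct values run from 0.098 to 0.855. At the null rate the printed figure is 4.6 times the correct one (0.4557 / 0.0984), and at the target rate it overstates power by 0.059. The stopping row is right and the original design is sound.

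For the 10-patient trial, 0.456 to 0.914 are valid only as the chance of not being stopped for futility. A result of fewer than 2 successes still has a stated meaning (ineffective); a result of 2 or more has none. The calculation assumes independent binomial responses, as 16.33 does, and exactly 10 and 28 evaluable patients at the two looks.

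**What to change.** In 16.33:

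- Relabel the printed row as the probability of continuing past the interim (at least 2 of 10).
- Add a row for the probability of declaring promising activity under the two-stage rule: 0.098, 0.280, 0.511, 0.716, 0.855.
- Mark that new row and the .10 sentence as applying to the original 28-patient design only, not applicable since Amendment 4.

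In 16.22, replace the instruction to keep accruing with a statement for the 10-patient trial: fewer than 2 successes means ineffective; 2 or more means only that the regimen was not futile, a bar passed 45.6% of the time at a true rate of 15% and 91.4% at 35%. Report the proportion with the interval 16.41 already provides for ("Confidence intervals for the true success proportion will be calculated according to the approach of" the named method), and make no claim of promising activity at 10% error.

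The cost is some wording and one table row. No patients, visits or analyses are added. The only loss is that the stated power figures look less favourable.

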16.4 Analysis Plan

16.41 Primary Outcome Analysis: The mSWAT score at baseline and cycle 9 will be used for change in baseline calculations. All calculated values will use the last-observation-carried forward for any participants who withdraw, are lost to follow up, or exit the study per protocol. The proportion of successes will be estimated by the number of successes divided by the total number of evaluable patients will be analysed using Mann-Whitney U for nonparametric data and the student t-test. Confidence intervals for the true success proportion will be calculated according to the approach of Duffy and Santner (Duffy D 1987).

16.42 Secondary Outcome Analysis: These analyses will include all patients meeting the eligibility criteria who have signed a consent form and have begun treatment, including patients who fail to achieve a complete or partial response.

Adverse Events: All eligible patients that have initiated treatment will be considered evaluable for assessing adverse event rate(s). The maximum grade for each type of adverse event will be recorded for each patient, and frequency tables will be reviewed to determine patterns. Additionally, the relationship of the adverse event(s) to the study treatment will be taken into consideration.

Response Rates:

Changes in mSWAT scores from baseline will be evaluated at cycle 9. Summary statistics will be calculated.

Patients will be assigned response based on the mSWAT criteria in section 11.0. Proportions of patients will be calculated and described using summary statistics. Proportions of interest are patients having CR, CR90 and PR; patients having stable subcutaneous disease; patients having progressive cutaneous disease; and patients having an overall systemic response rate.

Progression free survival time is defined for all evaluable patients as the time from registration to relapse or death due to any cause. Patients are censored if they have not achieved a progression at the time of analysis. The distribution of progression-free survival will be estimated using the method of Kaplan-Meier. In addition, the progression-free survival rate at 5 years after registration will be reported.

Duration of response is defined for all evaluable patients who have achieved a CR, CR90 or PR as the date at which the patient's objective status is first noted to be a CR, CR90 or PR to the earliest date relapse is documented. The distribution of duration of complete response will be estimated using the method of Kaplan-Meier.

Time to response is defined as the time from registration to CR, CR90 or PR. The distribution of survival time will be estimated using the method of Kaplan-Meier (Kaplan and Meier 1958).

Overall survival time is defined as the time from registration to death due to any cause. Patients are censored if they are alive at the time of analysis. The distribution of survival time will be estimated using the method of Kaplan-Meier (Kaplan and Meier 1958). In addition, the overall survival rate at 2 years after registration will be reported.

Additional Analyses: All endpoints may be analysed using patient characteristics to explore possible associations of demographics with the endpoints. Possible characteristics include clinical stage, gender and prior treatments.

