16.7 Inclusion of Women and Minorities

16.71 This study will be available to all eligible patients, regardless of race, gender, or ethnic origin.

16.72 There is no information currently available regarding differential effects of this regimen in subsets defined by race, or ethnicity, and there is no reason to expect such differences to exist. Therefore, although the planned analysis will, as always, look for differences in treatment effect based on race, the sample size is not increased in order to provide additional power for subset analyses.

16.73 The geographical region served by MCCC has a population which includes approximately 3% minorities. Based on prior MCCC studies involving similar disease sites, we expect about 3-5% of patients will be classified as minorities by race and about 30% of patients will be women. Expected sizes of racial by gender subsets are shown in the following table:

Accrual Estimates by Gender/Ethnicity/Race

Ethnic Category	Sex/Gender			
	Females	Males	Unknown	Total
Hispanic or Latino	5	4	0	9
Not Hispanic or Latino	11	11	0	22

Ethnic Category	Sex/Gender			
	Females	Males	Unknown	Total
Ethnic Category: Total of all subjects	16	15	0	31
Racial Category				
American Indian or Alaskan Native	0	0	0	0
Asian	0	0	0	0
Black or African American	4	5	0	9
Native Hawaiian or other Pacific Islander	0	0	0	0
White	12	10	0	22
Racial Category: Total of all subjects	16	15	0	31

Ethnic Categories: **Hispanic or Latino** – a person of Cuban, Mexican, Puerto Rico, South or Central American, or other Spanish culture or origin, regardless of race. The term “Spanish origin” can also be used in addition to “Hispanic or Latino.”

Not Hispanic or Latino

Racial Categories: **American Indian or Alaskan Native** – a person having origins in any of the original peoples of North, Central, or South America, and who maintains tribal affiliations or community attachment.

Asian – a person having origins in any of the original peoples of the Far East, Southeast Asia, or the Indian subcontinent including, for example, Cambodia, China, India, Japan, Korea, Malaysia, Pakistan, the Philippine Islands, Thailand, and Vietnam. (Note: Individuals from the Philippine Islands have been recorded as Pacific Islanders in previous data collection strategies.)

Black or African American – a person having origins in any of the black racial groups of Africa. Terms such as “Haitian” or “Negro” can be used in addition to “Black or African American.”

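### Section 16.41 assigns Mann-Whitney U and an unspecified t-test to a single-arm yes/no response proportion, which neither test suits

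*Combined protocol and SAP*

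**What the plan says.** Section 16.11 defines success as a cutaneous CR, CR90 or PR by mSWAT, so each patient contributes a yes or a no. There is one agent and one regimen (Section 7.1), and Section 5.0 lists no stratification or grouping factor. Section 16.21 sets 15% as the rate at which the regimen counts as ineffective and 35% as the rate worth pursuing. Section 16.33 rests the design on the binomial: "Assuming that the number of successes is binomially distributed, the significance level is .10".

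Section 16.41 is the primary analysis. It opens with a continuous quantity: "The mSWAT score at baseline and cycle 9 will be used for change in baseline calculations". It then defines the success proportion as successes over evaluable patients, and the same sentence runs on to say that this "will be analysed using Mann-Whitney U for nonparametric data and the student t-test". The next sentence gives an interval: "Confidence intervals for the true success proportion will be calculated according to the approach of Duffy and Santner". No confidence level is stated.

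Group comparisons appear only elsewhere. Section 16.42, under additional analyses, says "All endpoints may be analysed using patient characteristics to explore possible associations of demographics with the endpoints", and Section 16.72 says "although the planned analysis will, as always, look for differences in treatment effect based on race".

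Amendment 4 stops accrual at 10 patients. Section 16.1 adds that "the study power and type I error will not be appropriate for the analysis" and that the analysis will be made at the interim step. Sections 16.23 and 16.24 are marked as no longer applicable. Section 16.41 carries no such mark and remains in force.

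**The concern.** As written, both tests are attached to one proportion from one sample. Mann-Whitney U compares two independent samples, so it cannot be run on this quantity at all. A t-test could be forced onto the 0/1 data as a one-sample test, but 16.41 does not say so, and the design figures in 16.33 do not come from it.

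These are the only tests named for the primary endpoint. The null rate and a 0.10 level can be found in 16.21 and 16.33, but nothing links them to these tests. An analyst would have to drop the tests, or choose the variable, the form of t-test and the sidedness, possibly after seeing the data. A p-value reported under 16.41 could then not be traced to a pre-specified hypothesis.

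**Working it through.** **Inputs.** Null rate 0.15 and target rate 0.35 (16.21); 10 evaluable patients, with continuation at 2 or more successes (16.22); final rule of at least 7 of 28, now void (16.23); level 0.10 (16.33); accrual ending at 10 (16.1, 16.31).

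**1. Reproduce the plan's own figures.** With X ~ Bin(10, p), P(X ≥ 2) = 1 − (1−p)^10 − 10p(1−p)^9.

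- At p = 0.15: 1 − 0.1969 − 0.3474 = 0.456.
- At p = 0.35: 1 − 0.0135 − 0.0725 = 0.914.

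The other columns of the 16.33 table also match (0.624, 0.756, 0.851). For the original two-stage design, the sum over x ≥ 2 of P(X₁ = x) · P(X₂ ≥ 7 − x), with X₂ ~ Bin(18, p), gives 0.0984 at 15% and 0.8548 at 35%. The plan states 10% and 85%. Every stated operating figure therefore comes from binomial counts, and none from a rank test or a t-test.

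**2. Mann-Whitney U on the success proportion.** It needs two independent samples. Section 16.41 supplies one, so the statistic has no value.

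**3. One-sample t-test against 15%.** With x successes in 10 and p̂ = x/10, the sample variance is (10/9)p̂(1−p̂). Hence t = (p̂ − 0.15) / √(p̂(1−p̂)/9) on 9 degrees of freedom. At x = 4, t = 0.25/√(0.24/9) = 1.531. The exact one-sided p-value is P(X ≥ x | 0.15).

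| Successes of 10 | Exact, one-sided | t | t-test, one-sided | t-test, two-sided |
|---|---|---|---|---|
| 1 | 0.803 | −0.500 | 0.685 | 0.629 |
| 2 | 0.456 | 0.375 | 0.358 | 0.716 |
| 3 | 0.180 | 0.982 | 0.176 | 0.352 |
| 4 | 0.050 | 1.531 | 0.080 | 0.160 |
| 5 | 0.010 | 2.100 | 0.033 | 0.065 |
| 6 | 0.001 | 2.756 | 0.011 | 0.022 |

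For 7 to 9 successes every p-value is below 0.006. At 0 and 10 the standard deviation is zero and t is undefined.

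**4. Compare at 0.10.** The one-sided t-test and the exact test fall on the same side for 1 to 9 successes. The two-sided t-test differs from the exact test at one count only, 4 of 10. That count has probability 210 · 0.15⁴ · 0.85⁶ = 0.040 at a true rate of 15%, and 210 · 0.35⁴ · 0.65⁶ = 0.238 at 35%.

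**5. Alternative reading: mSWAT change.** Baseline and cycle 9 scores come from the same patients. Mann-Whitney U treats the two sets as independent and is still the wrong test. A t-test would be usable only if specified as paired, which 16.41 does not do.

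**6. Alternative reading: subgroups.** The looks by patient characteristics (16.42) and by race (16.72) do form groups. They sit outside 16.41 and are not the primary analysis.

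**The case against.** The strongest reply is that almost nothing turns on the clause. The estimator and interval in 16.41 suit a binary endpoint, the study is to be analysed at the interim step by the 16.22 count rule, and neither depends on a test. The 4-of-10 discrepancy requires a level and a sidedness that 16.41 does not set, and 16.22 is passed at 4 of 10 whichever test is run. The 0.238 is the chance of a particular count, not of a wrong decision. All of this stands, and it limits the weight of the point.

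A second reply is that the sentence is garbled, with two predicates run together, and may have been meant for mSWAT change. On that reading a paired t-test would be acceptable. That is fair as to intent. It does not save Mann-Whitney U, and the text still has to be repaired before an analyst can follow it.

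Third, the null and the 0.10 level do appear in 16.21 and 16.33, so the analyst is not wholly without guidance. That is true, but the missing link between them and the named tests is the defect.

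**Conclusion.** The concern holds. Section 16.41 names one test that cannot be run on the primary endpoint and another with no stated form, while the design is binomial throughout. Neither charitable reading makes the clause correct, and Amendment 4 leaves it in force.

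The consequence is an ambiguous primary test. The sample size, success count, stopping rule and interval are not affected, and no planned decision changes. The numerical comparison assumes 10 evaluable patients, a one-sample t-test against 15% and the plan's 0.10 level as the yardstick; 16.41 itself states none of the last three. It should be fixed because it is the primary analysis and the repair is small.

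**What to change.** Delete both tests from 16.41, leaving the primary result as the number of patients with CR, CR90 or PR at cycle 9 divided by the number evaluable. Keep the Duffy and Santner interval and state its confidence level.

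If a p-value is wanted, specify a one-sided exact binomial test against 15% and label it descriptive because of Amendment 4. If mSWAT change is to be tested, name a paired method: Wilcoxon signed-rank or paired t-test.

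Two secondary edits could go into the same revision:

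- If 16.22 is applied to the 10 patients, say that it is a futility rule only. Two or more successes occur with probability 0.456 at a true rate of 15%, so passing is not evidence of activity. The passing branch, "Otherwise, if the number of successes is at least 2, we will continue accrual", can no longer occur.
- In 16.21 the null is worded for complete response. It should refer to the success proportion (CR, CR90 or PR). No count or threshold depends on this.

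The cost is wording in Section 16. No count, threshold, visit or sample size changes. Because Section 16 is part of the protocol, the edit is an amendment and needs IRB approval before implementation under Section 6.8c.
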